2. STUDY DESIGN

2.1 Overview

This will be a randomized controlled trial. Data will be collected by asking patients to fill out a demographic questionnaire and a baseline visual analog scale rating their nausea, pain and anxiety at their clinic appointment 1-2 days prior to their procedure. Patients will then take either ondansetron or a placebo 30 minutes prior to taking doxycycline the night before their procedure. They will then fill out a symptom/medication log recording their symptoms from the time that they take the study medication to the time that they present for their procedure. When they present for their procedure, patients will fill out a second identical visual analog scale rating nausea, pain and anxiety. The primary outcome is nausea and vomiting after taking the study drug and doxycycline the night prior to surgery. Doxycycline prophylaxis the night prior to surgery is the current standard of care. Eligible patients will be enrolled over the course of two years.

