5. METHODS AND STUDY PROCEDURES

Patients will be approached for participation in the randomized controlled trial after they have completed their pre-operative consultation and have already consented for pregnancy termination. Once patients are consented, they will be randomized to either the placebo or ondansetron group. The study medication will be taken 30 minutes prior to doxycycline medication the night prior to the pregnancy termination. Doxycycline prophylaxis is currently the standard of care, and is not part of the study procedure. Randomization scheme will be generated by computer generated random number blocks using a 1:1 ratio. Allocation will be done by sequentially numbered opaque sealed envelopes. The pharmacy will be compounding the study medication so that it looks exactly like the placebo tablet, in appearance, texture and smell. Once consented and randomized during their clinic visit 1-2 days before the procedure, patients will fill out a demographic questionnaire regarding their age, race, relationship status, income and education level, pregnancy history, gestational age, and symptoms of nausea and vomiting thus far in the pregnancy. This questionnaire will also include questions regarding cigarette and THC use, as well as any diagnoses of gastroesophageal reflux disease or hyperemesis gravidarum. They will then fill out a baseline visual analog scale rating their nausea, pain and anxiety, prior to leaving the office.

The study coordinator will also conduct a chart review for select information. For participants enrolled prior to this version date, it will be retrospectively collected. For participants after this protocol version date, it will be collected at the time of enrollment. They will collect Gestational Age at Procedure Date (weeks/days), Cervical Preparation (Mifepristone Y/N) (Misoprostol Y/N) (Cervical Dilators Y/N, IF Y, How Many?) Genetic Indication for Termination? (Y/N).

The patients will then be given a symptom/medication log to take home. The patients will use the log to record symptoms they experience from the time they take the ondansetron or placebo to the time that they present for their procedure. The log will include the timing of the study medication, doxycycline, whether the doxycycline was taken with food (and the time of/type of food if applicable), pain medications, and misoprostol. The log will also include the time of nausea and vomiting, and the severity of the nausea and pain (if applicable).

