6. CONCOMITANT AND DISALLOWED MEDICATIONS

As per standard of care (and irrespective of the research study), in addition to doxycycline, patients will take 400 mcg of misoprostol buccally 3 hours before their procedure. It is also standard of care that patients are able to take either Ibuprofen or Tylenol #3 as needed for pain before their procedure. They will also be permitted to take any other medications that they take on a daily basis. None of these medications are part of the research protocol. They will be instructed not to take any antiemetics. We will record any medications that are used.

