10.5 Alternatives to Participation

Patients who decline to participate in the study will receive the standard of care at our clinic for termination of pregnancy, which involves the use of doxycycline as a prophylactic antibiotic the night before the procedure, as well as misoprostol the morning of the procedure. They will also be able to take Ibuprofen or Tylenol #3 for pain. They will not fill out any surveys or logs or take the study drug.

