13.2 Planned Statistical Analysis

Our primary outcome of vomiting, will be analyzed using chi-square analysis. All dichotomous outcomes will be analyzed using chi-square analysis. Continuous variables will be examined using t-tests. If demographic variables are found to be confounders with significance, they will be placed into a logistic regression model. SPSS software will be used for statistical analysis.

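### Must the primary analysis separate symptoms before the morning misoprostol from symptoms after it?

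*Combined protocol and SAP*

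**What the plan says.** Section 2.1 defines the outcome by its start: "The primary outcome is nausea and vomiting after taking the study drug and doxycycline the night prior to surgery". It gives no end. In the same section, patients keep a log "recording their symptoms from the time that they take the study medication to the time that they present for their procedure", and section 5 repeats that period: patients are to "record symptoms they experience from the time they take the ondansetron or placebo to the time that they present for their procedure". Section 13.2 adds only the test: "Our primary outcome of vomiting, will be analyzed using chi-square analysis". It mentions neither a window nor misoprostol, and its only adjustment is for demographic confounders.

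Section 6 states that "patients will take 400 mcg of misoprostol buccally 3 hours before their procedure", and section 10.5 places it on the morning of the procedure ("as well as misoprostol the morning of the procedure"). According to section 5, the log records when misoprostol was taken, and "The log will also include the time of nausea and vomiting". The data needed to divide the period at misoprostol would therefore be on the log, but no planned analysis uses them.

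Section 5 also lists a chart-review item for misoprostol, yes or no. Of the chart items it says: "For participants after this protocol version date, it will be collected at the time of enrollment".

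**The concern.** The background in section 1.2 asks whether an antiemetic given before doxycycline reduces the nausea and vomiting associated with that drug. If the outcome runs to presentation, it also counts events that begin after a further drug has been taken the next morning. The log's entry for misoprostol time suggests that some patients are expected to take it before they arrive.

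Two things could be at stake. First, if ondansetron has no effect on the later events, they dilute the treatment contrast and cost power. Second, if the end of the window is settled only after results by arm are known, the choice is open to criticism. The remedy looks cheap, because both times are already collected.

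**Working it through.** **1. The plan's own figure.** Section 13.1 takes 30% vomiting on placebo, a 50% decrease (to 15%) and 80% power, and gives 122 per arm. Alpha is not stated; I assume 5%, two-sided. With pooled variance and mean proportion 0.225:

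n = [1.96·√(2·0.225·0.775) + 0.842·√(0.30·0.70 + 0.15·0.85)]² / 0.15² = 120.5, so 121.

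That is one patient from the stated figure. Exact power of the Pearson chi-square test, by enumerating two binomials, is 81.3% at 122 per arm and 88.3% at 150.

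**2. Inputs the documents do not give.** Let q be the share of placebo patients with an outcome event after misoprostol and before arrival. Let r be the ratio of that risk on ondansetron to that on placebo. Neither appears in the documents, nor does arrival time relative to misoprostol. I assume q = 2%, 5% and 10%, r = 1, 0.75 and 0.5, independence of earlier and later events, and a halving of earlier events by ondansetron.

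**3. Model A: the 30% excludes the later events.** In the full window, placebo = 1 − 0.70(1 − q) and ondansetron = 1 − 0.85(1 − rq). For q = 5% and r = 1 this gives 33.5% against 19.25%. Exact power at 122 per arm:

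| | q = 2% | q = 5% | q = 10% |
|---|---|---|---|
| Window to misoprostol | 81% | 81% | 81% |
| Full window, r = 1 | 78% | 72% | 64% |
| Full window, r = 0.75 | 80% | 79% | 77% |
| Full window, r = 0.5 | 83% | 85% | 88% |

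**4. Model B: the 30% already includes the later events.** The earlier placebo risk is p₀ = 1 − 0.70/(1 − q), which is 28.6%, 26.3% and 22.2%. Ondansetron gives p₀/2 in the window to misoprostol and 1 − (1 − p₀/2)(1 − rq) in the full window, against 30% on placebo. Exact power at 122 per arm:

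| | q = 2% | q = 5% | q = 10% |
|---|---|---|---|
| Window to misoprostol | 79% | 75% | 66% |
| Full window, r = 1 | 75% | 64% | 44% |
| Full window, r = 0.75 | 78% | 72% | 62% |
| Full window, r = 0.5 | 80% | 79% | 78% |

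**5. Break-even.** At 122 per arm the two windows have equal power at r = 0.643, 0.652 and 0.666 (model A) and r = 0.647, 0.662 and 0.691 (model B). The full window loses power only if ondansetron cuts later events by less than about 31% to 36% (1 − 0.691 to 1 − 0.643). Above that it gains.

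**6. Effect on the estimate.** With r = 1, a true 50% reduction before misoprostol would appear in the full window as 46.8%, 42.5% and 36.5% (model A) or 46.7%, 41.7% and 33.3% (model B).

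**7. Which window the text supports.** The definition in section 2.1 starts after study drug and doxycycline, and the only recording period in the plan ends at presentation. Read together, they give a complete window. The hypothesis in section 2.2 concerns nausea and vomiting in these patients without restriction by cause. The anesthesia argument in section 1.2 concerns any symptoms before surgery. Both fit the full window.

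**The case for a change.** The strongest case for a change is that the window decides which question is answered. Section 1.2's wording about doxycycline leans towards symptoms before misoprostol, section 2.2 leans towards all symptoms before surgery, and the analysis section does not choose. With q = 10% and no ondansetron effect on later events, full-window power at 122 per arm could be as low as 64% or 44%, depending on the model. One sentence and one extra analysis would close the matter, with no new data item.

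Part of this stands. Section 13.2 gives no end point, and the logged misoprostol time is unused. Stating the end point before unblinding would do no harm. It is also true that the reference in section 2.1 to the night before more naturally describes when the drugs are taken than when symptoms count, so it does not by itself close the window.

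The rest does not carry the case. Nothing in the documents says that misoprostol causes nausea or vomiting, so they do not set it apart from the pain medicines that are also on the log or from the other cervical preparation. A cut at a clock time would not assign cause, and it would drop late episodes that doxycycline may have produced. It would also rely on times logged at home, which section 2.2 warns may not be filled in. The low power figures come from one corner of an assumed grid; another part of the same grid favors the full window.

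**Conclusion.** No change is needed. The plan omits the end of the outcome period, but an analyst would take it from the log: events after study drug and doxycycline, up to presentation. That comparison is not biased between arms, because allocation is random and misoprostol is standard care irrespective of the study. It also answers a question that the protocol itself poses.

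Splitting at misoprostol trades a narrower outcome against fewer events and dependence on logged times. In the illustration at 122 per arm, with q between 2% and 10%, the full window differs from the window to misoprostol by between 22 percentage points less power (model B, q = 10%, r = 1: 44% against 66%) and 12 points more (model B, q = 10%, r = 0.5: 78% against 66%). Both extremes rest on assumed values of q and r, on independence of earlier and later events, and on a two-sided 5% test. If patients arrive before taking misoprostol, the windows coincide and the difference is nil. An analysis limited to events before misoprostol is a reasonable optional extra from data already held, but the primary analysis does not depend on it.

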5.1 Safety Assessments

A comprehensive medical history will be obtained at the patient's clinic visit, and a physical exam will be performed as well to ensure that patients are not only fit and able to undergo their procedure, but also to participate in the study.

5.2 Assessment of Subject Compliance

Compliance with the demographic questionnaire and baseline visual analog scale will be assessed by nature of them both being filled out and turned in at clinic.

Compliance with taking the study medication will be assessed by asking the patient if and when they took either the ondansetron or placebo when they present for their procedure. Compliance with completing the symptom/medication log will be assessed by asking the patient to turn in their log when they present for their procedure.

Compliance with the second visual analog scale will be ensured by asking the patient to complete it in the hospital before their procedure.

5.3 Data & Specimen Banking for Future Research Use

Blood samples that will be obtained from subjects on the morning of their procedure will be kept for future research use. The subjects have their blood drawn routinely the morning of their procedure as a standard of care in order to obtain a complete blood count and type and screen. Blood samples will be stored for the purpose of potentially comparing serum levels of doxycycline in the future. The samples will be stored in a secure location at the University of Rochester. the Study Coordinator, [name], [name] and [name] will have access to the samples. The samples will not be released to investigators outside the study team. The samples will be stored for 5 years and will be destroyed after that. The samples will be coded to allow subjects to be identified so as to potentially correlate their reported nausea/vomiting scales to serum levels of doxycycline. Subjects may withdraw the sample at any time should they choose to. They simply must contact the Study

Coordinator to do so. Subjects will not be re-contacted regarding the banked samples.

5.4 Costs to the Subject

Subjects will not incur any additional costs by participating in this study.

5.5 Payment for Participation

Patients will not be reimbursed to participate in this study.

6. CONCOMITANT AND DISALLOWED MEDICATIONS

As per standard of care (and irrespective of the research study), in addition to doxycycline, patients will take 400 mcg of misoprostol buccally 3 hours before their procedure. It is also standard of care that patients are able to take either Ibuprofen or Tylenol #3 as needed for pain before their procedure. They will also be permitted to take any other medications that they take on a daily basis. None of these medications are part of the research protocol. They will be instructed not to take any antiemetics. We will record any medications that are used.

7. SUBJECT WITHDRAWALS

Patients will be withdrawn from the study if they themselves request to do so, or if they fail to take the study medication or the doxycycline. They will not be withdrawn if they fail to complete the demographic questionnaire, the baseline visual analog scale, the symptom/medication log, or the second visual analog scale. In the event that a patient does not complete one of these forms, The Study Coordinator will help her complete them. No additional study activities will be completed prior to subject withdrawal.

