2.2 Rationale for Study Design

A randomized controlled trial was selected in order to study ondansetron's effect on the rates of nausea and vomiting in our particular population, so that patients will not know if they are being given ondansetron or placebo before taking doxycycline. Some potential barriers that are expected in the study include that the patients may not fill out their symptom/medication log as this will be done at home. There are approximately 450 patients undergoing surgical termination of pregnancy at the

University of Rochester each year. In order to attain our goal sample size of 300 patients, we would have to enroll a large portion of the total patients. The primary hypothesis is that the rate of nausea and vomiting in patients undergoing surgical pregnancy termination will be decreased in the group receiving ondansetron versus the group receiving placebo.

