8.2 Dosage of Study Drug

The dosage of ondansetron will be 8 mg, orally, once.

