8.5 Subject Withdrawal of Study Drug

Subjects may stop study drug and still continue to be followed in the study.

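### Section 7 withdraws randomised patients who miss either drug and section 13.2 names no analysis set, so the primary comparison may be conditioned on missed doxycycline

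*Combined protocol and SAP*

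**What the plan says.** Patients are randomised in clinic 1-2 days before the procedure, before taking either drug (section 5). The order is then fixed: "The study medication will be taken 30 minutes prior to doxycycline medication the night prior to the pregnancy termination".

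Section 7 withdraws a patient who asks to leave, "or if they fail to take the study medication or the doxycycline". Section 8.5 reads: "Subjects may stop study drug and still continue to be followed in the study". Section 8.2 reads: "The dosage of ondansetron will be 8 mg, orally, once".

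Section 2.1 defines the outcome by intake of both drugs: "The primary outcome is nausea and vomiting after taking the study drug and doxycycline the night prior to surgery". The home log opens earlier. In it patients "record symptoms they experience from the time they take the ondansetron or placebo to the time that they present for their procedure". Section 13.2 calls the primary outcome simply vomiting and assigns it a chi-square test. Neither that section nor any other says which patients are analysed or how withdrawn patients count. Section 13.1 deals with withdrawal and non-compliance only by raising 122 to 150 per arm.

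On intake, section 5.2 has staff ask at presentation whether and when the study tablet was taken. It does not mention doxycycline. The log covers it: "The log will include the timing of the study medication, doxycycline, whether the doxycycline was taken with food".

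**The concern.** Four gaps combine.

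- **Conflicting rules.** With one dose there is no course to stop part-way. A patient who does not take the tablet is withdrawn under section 7 and, on the natural reading, followed under section 8.5.
- **Unnamed analysis set.** Two analysts could use different denominators for the primary test and each claim to follow the plan.
- **Selection through doxycycline.** A patient who is nauseated or vomits in the half hour after the tablet may not take doxycycline. The trial drug is an antiemetic, so it may change how often this happens. Excluding such patients conditions the comparison on a post-randomisation event that treatment can affect. If ondansetron works, more placebo patients would be lost this way, and they would tend to be the symptomatic ones.
- **No outcome without doxycycline.** As section 2.1 is worded, a patient who takes no doxycycline has no outcome value.

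At stake are the size of the estimated effect and the power to detect it.

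**Working it through.** **Inputs.** From section 13.1: 30% on placebo, a 50% decrease to 15%, 80% power, 122 per arm needed and 150 enrolled. From section 5: 1:1 allocation. The documents state no alpha; two-sided 0.05 is assumed throughout. They also give no missed-dose rate, so every share below is an assumption.

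**1. The plan's own figure.** Pooled-variance formula, mean rate 0.225:

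n = [1.960·√(2·0.225·0.775) + 0.842·√(0.30·0.70 + 0.15·0.85)]² / 0.15² = 120.5, so 121 per arm. The stated 122 is reproduced to within one patient. The powers below come from exact enumeration of two binomials with the uncorrected Pearson chi-square. With no loss, power is 81.3% at 122 per arm and 88.3% at 150. The implied allowance is 1 − 122/150 = 18.7%.

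**2. Exclusion related to outcome (the doxycycline route).** Suppose a share w of would-be events in an arm with rate p is dropped. The rate among those kept is p(1−w) / [p(1−w) + 1−p], and the number kept is 150(1−wp).

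With w = 0.25 on placebo, the rate is 0.225/0.925 = 24.3% in about 139 patients. Then:

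| Share dropped on ondansetron | Ondansetron rate (n) | Difference | Power |
|---|---|---|---|
| 25% (same) | 11.7% (144) | 12.6 points | 80% |
| 12.5% (half) | 13.4% (147) | 10.9 points | 67% |
| 0% | 15.0% (150) | 9.3 points | 52% |

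With smaller placebo shares of 5/10/20%, power is 87/86/82% for the same share on ondansetron and 85/82/73% for half. If both arms have a 30% rate and the same share is dropped, the rejection rate stays at about 5%.

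**3. Exclusion unrelated to outcome.** If 5/10/18.7% of each arm are excluded at random, 142/135/122 per arm remain and power is 87/85/81%. This is the case that section 13.1 allows for. It also fits patients who never take the study tablet: the tablets look identical, so while blinding holds, not taking one cannot depend on the arm.

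**4. Keeping everyone, 150 per arm.**

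- Missed study tablet: a share f of the ondansetron arm has the placebo rate, so its rate is 0.15 + 0.15f. For f = 5/10/18.7% this is 15.75/16.5/17.8%, with power 84/80/70%. About 136/153/191 per arm would be needed for 80%.
- Missed doxycycline: a share f of both arms has event rate b, so each rate becomes p(1−f) + bf. With b = 0, power is 86/84/79%. With b = 15%, it is 85/82/74%. The need for 80% power is 129-133, 138-146 and 157-175 per arm.

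**The case against.** The strongest reply is that including never-takers is a choice of estimand, not the repair of an error. For the study tablet this largely stands. Excluding those patients mainly costs sample size and gives no arm-dependent selection while blinding holds, whereas including them lowers power, from 81% to 70% at 18.7%. The selection argument rests on doxycycline alone.

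Other parts also stand:

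- Section 8.5 speaks of stopping, not of failing to take, and concerns only the study drug. The conflict depends on the single dose in section 8.2.
- The outcome is undefined as worded, not unmeasurable. The log starts at the study tablet, so symptoms before doxycycline can be recorded.
- If the same share of events is dropped in both arms, the relative effect is not weakened. At w = 25% the rate ratio is 11.7/24.3 = 0.48 against a planned 0.50. Only the absolute difference and the power fall.
- A reader might infer that doxycycline intake is known only from the home log, given the warning in section 2.2 that "patients may not fill out their symptom/medication log as this will be done at home". The documents do not support that. Section 7 has the coordinator help complete unfinished forms, and section 6 says that medications used will be recorded. The blood sample (sections 5 and 5.3) may also inform intake. What remains is that section 5.2 omits doxycycline although missing it triggers withdrawal.

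None of this answers the main point: section 7 is an explicit removal rule after randomisation, and nothing says how the removed patients enter the primary test.

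**Conclusion.** The point holds as an unspecified analysis set combined with a withdrawal rule that can depend on the outcome. It should be fixed before unblinding.

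Its size cannot be derived, because no missed-dose rate is given. The range of 80% to 52% power, against 88% with no loss, assumes that a quarter of would-be placebo events are dropped and that every dropped patient is a would-be event. Early symptoms are in truth only a marker, since the 30% in section 13.1 refers to patients who take doxycycline. The figures illustrate and do not bound the effect.

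Two stronger readings are tempting. One is that the plan is shown to be biased. It is not: exclusion from the primary test is implied by sections 13.1 and 13.2 but never stated, and the sentence in section 7 about no additional activities may mean only that there is no exit procedure. The other is that false-positive results become more likely. With no true effect and identical tablets, the documents give no mechanism for that. The likely direction, if ondansetron works, is towards no effect.

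**What to change.** - **Section 7:** record a missed study tablet or missed doxycycline as non-adherence rather than as withdrawal from follow-up. Still collect the log and the second visual analog scale at presentation. Reconcile the text with section 8.5.
- **Section 13.2:** make the primary analysis all randomised patients in their assigned arm. Add an adherent-only sensitivity analysis and report missed doses by arm.
- **Section 2.1:** define an outcome window that applies to every randomised patient, including those who miss either drug. State how symptoms after the pre-procedure misoprostol (section 6) are counted, since a window running to presentation can include them.
- **Section 5.2:** also ask at presentation whether and when doxycycline was taken.
- **Section 13.1:** state the power under the expected non-adherence.

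The practical cost is one added question and a written outcome definition; the patients already attend and the forms are already collected there. The statistical cost is dilution, as in step 4 of the working. At 150 per arm, all-randomised power stays near 80% or above for up to 10% missed doses. At 18.7% it falls to 70% for missed study tablets and to 74-79% for missed doxycycline, against 81% if the same share is excluded at random. At the 160 per arm in section 3.1.1, the missed-tablet figures for 5/10/18.7% are 87/82/73%. No dosing or treatment rule changes.
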